12.3.8 Body Mass Index

At Visit 1 (Screening Visit), height (without shoes) will be measured and recorded, rounded to the nearest centimetre.

At Visits 1, 2 and 21-35, body weight (without overcoat and shoes) will be measured and recorded, rounded to the nearest kilogram. Body mass index will be calculated automatically, based on eCRF entries of height and body weight.

12.3.9 Laboratory Parameters for Evaluation of Subject Eligibility

At Visit 1 (Screening Visit) blood samples will be drawn for the purpose of measurement of the following laboratory parameters: HIV, CD4⁺, HIV viral load, HBsAg, HBeAg, HBV DNA and HCV RNA.

As described in [Section 12.3.1](#), a blood sample will be drawn at Visit 1 (Screening Visit) for the purpose of measurement of FIX inhibitor by the local laboratory.

As described in [Section 12.2.6](#) at Visit 1 (Screening Visit) a blood sample will be drawn for the purpose of measurement of neutralizing antibodies to AAV5.

Furthermore, as described in [Section 12.2.4](#), Visit 1 blood and urine samples will be drawn for analysis of serum chemistry, haematology, coagulation and urine parameters.

For the purpose of evaluation of Exclusion Criterion 2, the Investigator will use the Visit 1 (Screening) laboratory result from the local laboratory. The Investigator will be informed by the central laboratory about the Screening laboratory results for the purpose of evaluation of Exclusion Criteria 3, 4, 5, 6, 8 and 9.

If pre-determination of subject eligibility is desired by the Investigator in advance of the conduct of the full screening visit (Visit 1), an additional visit can be performed during which a selection of laboratory parameters (neutralizing antibodies, HIV, CD4⁺, HIV viral load, HBsAg, HBeAg, HBV DNA and HCV RNA) can be measured (see [Table 5-2](#), additional visits). When pre-determination of subject eligibility is established and the subject continues

Clinical Trial Protocol

Trial ID: CT-AMT-060-01

uniQure

into the trial, a full screening visit (Visit 1) needs to be conducted (see [Table 5-1](#) and [Table 5-2](#), Visit 1), however if the timing of the additional visit is within 2 weeks of Visit 1 there is no need to repeat the laboratory parameters previously measured.

12.3.10 Further Testing of Subjects with a Suspected FIX Inhibitor

A subject is said to suffer from FIX inhibitors if tested positive for FIX inhibitors at 2 consecutive tests (as measured by the local laboratory), performed preferably within 2 weeks.

If a subject has confirmed FIX inhibitor and continues with no change to treatment type for 6 weeks and the FIX inhibitor test is negative after that time, the FIX inhibitor is classified as transient.

12.3.11 Laboratory Samples for Future Research

Additional blood samples for the purpose of potential future research in the haemophilia B disease area (including development and validation of assays to support efficacy assessments) will be drawn at screening (Visit 1), baseline (i.e. pre-IMP time point during Visit 2) and at the following time points after IMP administration: 5 weeks, 10 weeks, 26 weeks and 52 weeks (Visit 7, 12, 21 and 23).

These additional blood samples will only be drawn if separate informed consent is given by the subject. Subjects who do not wish to donate blood samples for the purpose of potential future research may still participate in the trial and will not be required to withdraw from the trial if they withdraw consent for the potential future research.

The procedures for the collection, processing, storage and shipment of these blood samples are described in the Laboratory Manual.

12.4 **General Information Regarding Laboratory Sampling and Results**

All laboratory assessments will be conducted at a central laboratory, except FIX activity assay for monitoring of subjects ([Section 12.3.1](#)), FIX inhibitor assay for monitoring of subjects and for eligibility check ([Section 12.3.1](#)) and liver enzymes (AST and ALT) ([Section 12.3.1](#)) which will be conducted locally.

Dates and times of sampling will be recorded.

Detailed procedures for the collection, processing, storage and shipment of laboratory samples are described in the Laboratory Manual. This manual as well as all material such as test tubes and labels will be provided by the coordinating central laboratory.

After the laboratory samples have been analysed, they will remain stored for potential re-analysis at any time during the trial to a maximum of up to 1 year after the trial has been completed, before being destroyed. Exceptions are the future research blood samples, which will be stored and used for medical research until there is no sample remaining.

Clinical Trial Protocol

Trial ID: CT-AMT-060-01

uniQure

The Investigator will be provided with laboratory results at regular intervals for review and sign-off. Any abnormality, judged by the Investigator as a clinically relevant worsening since the first measurement, i.e. at Visit 1 or Visit 2, should be reported as an AE, unless the laboratory abnormality is associated with an already reported AE.

Any report of erroneous results in the following parameters from Visit 21 and onwards should prompt that the subject is called in for an Additional Visit to have blood sample(s) drawn for the purpose of re-measurement:

- FIX activity measured at local laboratory
- FIX activity measured at central laboratory
- FIX inhibitors measured at local laboratory
- FIX inhibitors measured at central laboratory
- Coagulation parameters
- AST, ALT
- FIX recovery and incremental recovery.

The Additional Visit should preferably take place within 1 week after the report of the erroneous result(s).

12.5 Total Blood Volume

Blood samples will be collected for efficacy, safety and screening assessments. For each subject, the total blood volume in the first half year, including screening, is expected to be 1906 mL (excluding any additional visits). For the remaining 4.5 years of the study, the total blood volume is expected to be 684 mL. Therefore, the total blood volume for subjects completing the study will be 2590 mL. The maximum blood volume per additional visit (during tapering phase or any other time) is 130 mL.

13. Safety Reporting

13.1 Adverse Event Definitions

An adverse event (AE), an adverse drug reaction (ADR) and a serious adverse event (SAE) are defined according to [ICH Guideline E2A](#).

An AE is any untoward medical occurrence in a subject administered the IMP and which does not necessarily have a causal relationship with this IMP or the IMP administration procedure. An AE can therefore be any unfavourable and unintended sign (including an abnormal laboratory finding, see [Section 12.4](#)), symptom, or disease temporally associated with the use of the IMP including the IMP administration procedure.

An ADR is an untoward and unintended response to the IMP related to any dose administered. A causal relationship between the IMP and the AE is at least a reasonable possibility.

An SAE is any untoward medical occurrence that at any dose:

- Results in death
- Is life-threatening (this refers to an event in which the subject was at risk of death at the time of the event; it does not refer to an event that hypothetically might have caused death if it was more severe)
- Requires in-patient hospitalization or prolongation of existing hospitalization
- Results in persistent or significant disability or incapacity
- Is a congenital anomaly or birth defect
- Is judged medically important by the Investigator (this refers to an event, not resulting in any of the outcomes listed above, but may jeopardize the subject or may require intervention to prevent one of the other outcomes listed)

In the following situations, events are not defined as an AE:

- Medical or surgical procedure (e.g. endoscopy, appendectomy); the condition that leads to the procedure is an AE
- Anticipated day-to-day fluctuations of pre-existing disease(s) or condition(s) present or detected at the start of the trial that do not worsen
- Condition(s) for which pre-planned procedure(s) have been recorded at Visit 1, including hospitalization(s), unless the condition(s) for which the procedure and/or hospitalization was planned has worsened from the first trial related activity after the subject has signed the informed consent form
- Concomitant illness identified during the screening procedures will be recorded as medical history. However, whenever symptoms for these condition(s) worsen and/or become serious, then these events must be reported as an AE or SAE, as applicable.

13.2 Adverse Event Assessment Definitions

13.2.1 Severity

The Investigator should assess the severity of all AEs according to the following definitions:

- Mild: Awareness of symptoms, sign, illness or event that is easily tolerated.

Clinical Trial Protocol

Trial ID: CT-AMT-060-01

uniQure

- Moderate: Discomfort sufficient to cause interference with usual activity.
- Severe: Incapacitating with inability to work or undertake further normal activities.

Note the distinction between seriousness and severity: The term severe is used to describe the intensity of the event and a severe event is not necessarily serious (e.g. a severe headache would probably not constitute an SAE; however a mild myocardial infarction could constitute an SAE). The seriousness criteria serve as a guide for defining regulatory reporting obligations.

If an AE changes severity over time, the severity of maximum intensity should be reported.

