Intravenous administration of a liver-directed AAV vector might lead to transaminase elevation. Previous clinical trials have shown that potential elevations in liver enzymes react promptly with normalization after administration of glucocorticoids. Subjects in the trial will be monitored twice weekly during the first 12 weeks after infusion of AAV5-hFIX for the occurrence of transaminase elevations, which may warrant the initiation of a corticosteroid treatment protocol.

Risks to third parties and the environment related to shedding via body fluids

The AAV vector will distribute systemically and small amounts of vector DNA have been observed in previous non-clinical and clinical studies in secreta and excreta, especially saliva and urine, for a limited period of time. The vector is non-pathogenic and cannot replicate. Therefore, the risk for third parties such as family and health care personnel is considered marginal. Due to the incapacity of replication, the non-infectious nature of the shed DNA and the negligible amounts shed, the risk to the environment can be considered negligible. No specific containment or protection measures are deemed necessary.

Risk of vector DNA integration into the host genome

AAV vector genomes remain mainly episomal after transduction of the target cells with minimal integration into the mammalian genome and with no association with oncogenicity. Integration site analysis was carried out by non-restrictive Linear Amplification Mediated Polymerase Chain Reaction (nr LAM PCR) and subsequent high throughput sequencing on DNA extracted from the livers of both mouse and cynomolgus macaques after administration of AAV5-hFIX at various doses. There was no preferred integration in genes known to mediate malignant transformation or clonal dominance. Both episomal (concatemeric) and integrated forms of AAV5-hFIX were retrieved, but the sequences were present almost exclusively as non-integrated episomal forms. The retrieved integrants were randomly distributed throughout the host genome. No specific clustering was seen in cynomolgus macaque genome, while some level of clustering around active genes was seen in the mouse. There were no signs of *in vivo* clone selection in the animals. The risk of oncogenicity will be assessed clinically during the duration of the trial, see [Section 10.2.5](#).

Risk of germ-line transmission of vector DNA

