19.2.1 Trial Stopping Rules

As the trial is a one-dose trial, stopping rules are relevant only for the recruitment period. Independently of any changes to the recruitment, subjects who have already been dosed will be followed as per protocol to the end of trial.

Clinical Trial Protocol

Trial ID: CT-AMT-060-01

uniQure

The data monitoring committee will prior to dosing review data as detailed below and recommend whether:

- The next subject could be dosed
- Further data would be required before the next dosing
- No further dosing should take place i.e. subject recruitment is discontinued.

The following events may lead to a decision to pause dosing, i.e. stop subject recruitment to allow for evaluation and assessment of the implications of the event for further subject dosing:

1. A more than 5-fold increase in ALT, AST or both in one or more subjects after IMP administration which is not manageable by steroid rescue treatment implemented according to American Association for the Study of Liver Diseases (AASLD) guidelines. (Manns et al. 2010)
2. An SAE judged as probably or possibly related to the IMP and which pose either an immediate risks to subject's health or is likely to adversely affect the subject's health long term. This includes events classified as AEs qualifying for special notification (Brussels, 03/12/2009, ENTR/F/2/SF/dn D(2009) 35810; EMEA/CHMP/GTWP/60436/2007) as listed in Section 13.6, if these are judged as probably or possibly related to the IMP. The development of an inhibitor towards FIX in one subject is not a cause for stop of subject recruitment, however the development of an FIX inhibitor in more than one subject should lead to pausing of dosing and further investigations of causal relationship
3. Death of a subject, after having received the IMP, that is judged as related to the IMP
4. The occurrence of a malignancy at any point after gene transfer that is judged as probably or possibly related to the IMP.

Decision to start Cohort 2

If none of the events listed above have occurred the data monitoring committee may recommend that Cohort 2 can be initiated. If one or more of these events have occurred, dosing will be paused while the event(s) is/are further investigated including the implications for further dosing and dose level.

Decision to dose the next subject within a cohort

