Table 14.3.1.6 Frequency and Incidence of TEAEs of N	Mild Severity by MedDRA SOC as	nd PT - Full analysis	s set	
SOC PT	Cohort 1 (N=x) n (%) E	Cohort 2 (N=x) n (%) E	Total (N=x) n (%) E	
Any mild TEAEs	x (x.xx) x	x (x.xx) x	x (x.xx) x	
Infections and infestations Nasopharvneitis	x (x.xx) x	x (x.xx) x	x (x.xx) x	
Eye infection	x (x.xx) x	x (x.xx) x	x (x.xx) x	
Influenza	x (x.xx) x	x (x.xx) x	x (x.xx) x	
Sinusitis	x (x.xx) x	x (x.xx) x	x (x.xx) x	
Respiratory tract infection	x (x.xx) x	x (x.xx) x	x (x.xx) x	
Rhinitis	x (x.xx) x	x (x.xx) x	x (x.xx) x	
Oral herpes	x (x.xx) x	x (x.xx) x	x (x.xx) x	
Musculoskeletal and connective tissue disorders	x (x.xx) x	x (x.xx) x	x (x.xx) x	
Arthralgia	x (x.xx) x	x (x.xx) x	x (x.xx) x	
Back pain	x (x.xx) x	x (x.xx) x	x (x.xx) x	
Joint swelling	x (x.xx) x	x (x.xx) x	x (x.xx) x	
Groin pain	x (x.xx) x	X (X.XX) X	x (x.xx) x	
Tenosynovitis	x (x.xx) x	X (X.XX) X	x (x.xx) x	
Pain in extremity	x (x.xx) X	x (x.xx) x	x (x.xx) x	
Neck pain	x (x.xx) X	x (x.xx) x	x (x.xx) x	
F	x (x.xx) x	x (x.xx) x	x (x.xx) x	

TEAE: Treatment Emergent Adverse Event. MedDRA: Medical Dictionary for Regulatory Activities. SOC: System Organ Class. PT: Preferred Term.

N: Number of patients in Full Analysis Set (FAS). n: Number of patients with events. (%): Percentage of patients in FAS with Adverse Event. E: Number of Adverse Events. Cohort 1: AAV5-hFIX 5.0 x 10^12 gc/kg, Cohort 2: AAV5-hFIX 2.0 x 10^13 gc/kg

Adverse Events coded with MedDRA version 17.1

	arix
Trial ID: CT-AMT-060-01         Table Shells           EudraCT No: 2013-00557942-42         Table Shells	Final Version 05 Page 45 of 66

Table 14.3.1.6 Frequency and Incidence of TEAEs of Mild Severity by MedDRA SOC and PT - Full analysis set

SOC PT	Cohort 1 (N=x) n (%) E	Cohort 2 (N=x) n (%) E	Total (N=x) n (%) E	
Nervous system disorders	x (x.xx) x	x (x.xx) x	x (x.xx) x	
Headache	x (x.xx) x	x (x.xx) x	x (x.xx) x	
Dizziness	x (x.xx) x	x (x.xx) x	x (x.xx) x	
Nervous system disorder	x (x.xx) x	x (x.xx) x	x (x.xx) x	
Hypoaesthesia	x (x.xx) x	x (x.xx) x	x (x.xx) x	
General disorders and administration site conditions	x (x.xx) x	x (x.xx) x	x (x.xx) x	
Pyrexia	x (x.xx) x	x (x.xx) x	x (x.xx) x	
Influenza like illness	x (x.xx) x	x (x.xx) x	x (x.xx) x	
Peripheral swelling	x (x.xx) x	x (x.xx) x	x (x.xx) x	
Investigations	x (x.xx) x	x (x.xx) x	x (x.xx) x	
Hepatic enzyme increased	x (x.xx) x	x (x.xx) x	x (x.xx) x	
Transaminases increased	x (x.xx) x	x (x.xx) x	x (x.xx) x	

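### The AE severity scale has no laboratory criterion, and no planned table shows the size of ALT/AST rises by cohort

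*Protocol*

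**What the plan says.** Protocol 13.2.1 sets one scale for everything: "The Investigator should assess the severity of all AEs according to the following definitions". The three grades are:

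- "Mild: Awareness of symptoms, sign, illness or event that is easily tolerated"
- "Moderate: Discomfort sufficient to cause interference with usual activity"
- "Severe: Incapacitating with inability to work or undertake further normal activities"

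Protocol 13.1 defines an AE to include "any unfavourable and unintended sign (including an abnormal laboratory finding", and 12.4 asks for laboratory abnormalities to be reported as AEs when the investigator judges them a clinically relevant worsening. Neither the protocol nor the SAP names a separate grading scale for laboratory AEs.

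The primary endpoint is adverse events. Protocol 14.2.1 calls for summaries by severity. SAP 4.5.1 supplies them as pooled counts in Table 14.3.1.1 and by system organ class and preferred term in Tables 14.3.1.6 (mild), 14.3.1.7 (moderate) and 14.3.1.8 (severe).

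On the liver, protocol 6.7 says: "Intravenous administration of a liver-directed AAV vector might lead to transaminase elevation". Elsewhere the protocol does use size of rise. Section 13.6 makes an elevation above 1.5 times baseline an event for special notification, 11.2.3 refers to 1.5 to 2-fold of the Day 1 pre-IMP level, and the first stopping rule in 19.2.1 begins "A more than 5-fold increase in ALT, AST or both in one or more subjects after IMP administration" and then adds the condition that steroid rescue does not manage it.

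**The concern.** The scale measures how the patient feels and functions, whereas a transaminase rise is normally found by blood test. If the rise causes no symptoms, its size cannot affect the grade. The severity tables of a dose-ascending safety trial would then be uninformative on one aspect of liver safety that the two cohorts are meant to compare, namely whether the higher dose gives larger rises. A reader who sees hepatic enzyme terms only under Mild could take that as evidence that the rises were small, when it may reflect nothing more than the definitions.

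**Working it through.** The documents give no figure on this point to reproduce. The check sets the definitions against the outputs, then counts sampling time points.

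**1. Grade of a symptom-free rise.** Moderate needs discomfort that interferes with activity, and Severe needs incapacity. A rise without symptoms meets neither, which leaves Mild. Take an assumed baseline ALT of 25 U/L:

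| Peak (U/L) | Multiple of baseline | Grade, read literally |
|---|---|---|
| 40 | 40/25 = 1.6 | Mild |
| 130 | 130/25 = 5.2 | Mild |

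The assumed baseline does not matter, because the definitions contain no numerical limit. Rises on either side of the protocol's own figures (1.5, 2 and 5) get one grade.

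**2. Spread that the grade could hide.** In the AAV8 trial summarised in protocol Table 6-3, the four steroid-treated high-dose subjects had ALT peaks of 202, 36, 43 and 64 IU/L. The largest is 202/36 = 5.6 times the smallest. The documents do not say whether these rises caused symptoms. If they did not, this scale would grade all four alike.

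**3. What the other planned outputs show.**

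| Output | Shows a liver event | Shows size by cohort in a table |
|---|---|---|
| Tables 14.3.1.6 to 14.3.1.8 (severity) | Yes, by preferred term | No |
| Table 14.3.1.10 (special notification) | Yes; entry above 1.5 times baseline | No; a single threshold |
| Tables 14.3.1.3 and 14.3.1.5 (related, serious) | Yes | No |
| Serum chemistry listing (SAP 4.5.3.3) | Values with out-of-range flag | No |
| Figures 14.3.5.17 to 14.3.5.20 (ALT/AST profiles) | Yes, per patient and split by cohort | No; plots against the reference range |
| Local ALT/AST (SAP 4.6.5) | Listing | No |

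SAP 4.1 categorises laboratory values only as low, normal or high.

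**4. Local-only time points.** These are the scheduled post-dose ALT/AST measurements to week 26, from protocol Tables 5-2, 12-2 and 12-4:

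- Local: 24 hours (1), Visits 3 to 14 (12), Visits 3b to 14b (12), Visits 15 to 20 (6), Visit 21 (1). Total 1 + 12 + 12 + 6 + 1 = 32.
- Central: Visits 3 to 14 (12), Visits 16, 18 and 20 (3), Visit 21 (1). Total 12 + 3 + 1 = 16.
- Local only: 32 − 16 = 16, namely the 24-hour sample, Visits 3b to 14b, and Visits 15, 17 and 19.

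The profile plots are specified under serum chemistry, which is the central-laboratory panel (protocol 12.2.4). A peak caught at a local-only time point would therefore appear in a listing and in no planned table or chemistry plot of values.

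**The case against.** The strongest reply is that liver safety does not depend on the severity grade. Transaminase terms appear by cohort in several AE tables, and any elevation above 1.5 times baseline goes on an SAE form within 24 hours (protocol 13.4 and 13.6). The data monitoring committee sees liver parameters at its gateway meetings, and systemic corticosteroid use is tabulated by cohort in Table 14.3.7.1. With five to seven patients per cohort, individual ALT curves let a reader see most differences in size. No dosing decision uses the severity grade of an ALT rise. All of this stands, and it limits the point to reporting.

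Some stronger readings are tempting, and the documents do not support them:

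- *That the severity tables cannot show liver toxicity.* They list preferred terms, so they show that events occurred and how often. Only size is lost.
- *That a transaminase rise is the toxicity the protocol most expects.* Section 6.5 calls immune-mediated toxicity possibly the most important concern, but 11.2.3 rates the risk of significant enzyme disturbance as low. The cited experience points both ways. It was 4 of 6 at the high AAV8 dose, which if carried over would give a chance of at least one case in five subjects of 1 − (1/3)^5 = 0.996. It was 0 of 8 with AAV5 in porphyria, with a two-sided 95% upper limit of 1 − 0.025^(1/8) = 36.9%.
- *That every such rise will be graded Mild.* The investigator assigns the grade, and no text forbids another judgement. Departures from the wording would, however, make grades inconsistent between sites.
- *That the shells prove the effect.* "Hepatic enzyme increased" is pre-filled in the Mild and Serious shells, and enzyme terms are absent from the Moderate and Severe ones. That fits equally well with small rises. The Moderate shell also carries a lack-of-efficacy term that is not obviously discomfort, so literal grading cannot be assumed.
- *That a more than 5-fold rise alone triggers the stopping rule.* The rule also requires failure of steroid rescue and applies only during recruitment.

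**Conclusion.** The point holds as a gap in reporting. It is not a failure of safety oversight. The severity scale has no laboratory criterion, so the primary-endpoint severity tables cannot separate a rise just above 1.5-fold from one above 5-fold when neither causes symptoms. No other planned table gives size of rise by cohort. The plots narrow the gap but leave out 16 of 32 scheduled post-dose time points to week 26. Most of these lie a few days from a central sample, so the information lost may be modest.

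The conclusion rests on two assumptions: that investigators follow 13.2.1 as written, and that the chemistry plots use central values only, as the layout of SAP 4.5.3.3 and 4.6.5 implies. If local values are already in the plots, what remains is the missing table and the missing caution on how to read the severity tables.

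**What to change.** Leave the collected grades and 13.2.1 as they are. Protocol 20.1 treats the 52-week data as locked, so regrading is not practicable. In the SAP:

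1. **Add one descriptive table by cohort** (4.5.1 or 4.5.3.3): each patient's maximum post-dose ALT and AST, using central and local values, each divided by the same laboratory's Day 1 pre-IMP value. Both laboratories measure ALT and AST at that time point. Show the bands up to 1.5, above 1.5 to 2, above 2 to 5, and above 5. The protocol already contains these figures. Here they serve only as reporting bands and imply no clinical rule.
2. **Footnote Tables 14.3.1.1 and 14.3.1.6 to 14.3.1.8**, saying that the grade reflects symptoms and function and not the size of a laboratory change.
3. **Add local ALT/AST values to Figures 14.3.5.17 to 14.3.5.20**, marked by laboratory.

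The cost is one derived table, a footnote and a change to four figures, all from data already collected. The downside for the sponsor is that some rises now shown only as Mild will also appear in a less favourable band.
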